4.3. Exploratory Endpoints

- Time since randomization until improvement in oxygenation, (defined as independence from supplemental oxygen) during 28-day assessment period (or discharge, whichever comes earlier)**
- Number of days with hypoxia defined as SpO₂ < 93% breathing room air or the dependence on supplemental oxygen after randomization to Day 28 (or discharge, whichever comes earlier)**
- Time since randomization until absence of last fever (defined as 37.1°C or more) for more than 48h without antipyretics**
- **change in CRP levels between day 1 and day 6, and between day 1 and day 15 (or discharge in each case**
- **change in ferritin levels between day 1 and day 6, and between day 1 and day 15 (or discharge in each case).**
- Incidence of SARs/SUSARs during 28 days**
- Duration of hospital stay**
- Duration of hospital stay in survivors**
- **Change from baseline in 6-point ordinal scale to Day 6, Day 15 and D28 (by phonecall) post randomization**

- Percentage of participants reporting at least a 2-point improvement sustained to D28 or discharge
- AUEC/Time using the 6-point score recorded daily – up to D15, D28 and all data recorded
- Percentage of participants who record a 2-point improvement from baseline or discharge at D6, D15 and D28
- Percentage of participants not deteriorating according to the ordinal scale by 1 or 2 points on D6, D15 and D28
- 6-point Ordinal Scale at 6 and 15 days (or discharge whichever comes first) and day 28 (phone call), in relation to serum D-dimers and complement C5a levels at baseline

- Time since randomization until first use of high-flow oxygen devices or non-invasive mechanical ventilation or invasive mechanical ventilation or ECMO in non-ventilated patients (i.e. excluding patients who are ventilated within 24h prior to or after randomization) during 28-day assessment period
- duration of ventilator-free days after randomization to Day 28 (or discharge, whichever comes earlier)
- Duration of invasive mechanical (including ECMO) and non-invasive mechanical ventilation in ventilated patients
- Duration of ICU stay in patients that enrolled in trial on invasive or non-invasive mechanical ventilation for less than 24h prior to or after randomization during 28-day assessment period
- Duration of ICU stay in patients that enrolled in trial that were on invasive or non-invasive mechanical ventilation or high-flow oxygen devices within 24h prior to or after randomization during 28-day assessment period

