We will randomize patients with confirmed COVID19 with acute hypoxic respiratory failure (1. O₂ saturation below 93% on minimal 2l/min O₂ therapy; and/or 2. PaO₂/FiO₂ below 350 mmHg) to receive up to 14 days of SC Zilucoplan® on top of standard of care (active group A), or to receive standard of care treatment (control group B). Randomization will be done at a 2:1 ratio active: control group. In the active group A, patients will additionally receive daily antibiotics (daily 3rd generation cephalosporin IV while in hospital, followed by oral ciprofloxacin while discharged) as primary prophylaxis against meningococcal disease until 14 days after the last dose of Zilucoplan®. Control group B will receive standard of care and prophylactic antibiotics (3rd generation cephalosporin IV) for only 1 week (or until hospital discharge whichever comes first), to control for the effects of antibiotics on the clinical course of COVID-19. In case of allergies to these antibiotics, or on clinical indication, these antibiotics may be switched to antibiotics that also cover *Neisseria meningitidis*.

To measure the effectiveness of Zilucoplan® on restoring lung homeostasis, the **primary endpoint** of this intervention is **measuring change in oxygenation parameters** comparing baseline values (pretreatment) to values predose day 6 and to values at day 15 (or discharge whichever comes first) post-randomization in group A and group B and the differences in these values between group A and group B.

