11.1. Sample size calculation

The outcome(s) on which the sample size calculation is based upon, is the primary endpoint measurement of oxygenation, defined as ratio of PaO₂/FiO₂.

Sample calculation and power analysis have been performed by UCB. The target difference is the difference measured at the primary endpoint (day 6 and day 15 or discharge) between the control and the treated group. Given a sample size of 81 patients, 54 on Zilucoplan[®] and standard of care and 27 on standard of care there would be >85% power to show a significant difference from standard of care at the 2 sided 5% level if the true underlying treatment difference was an 80 point difference (25% of 320, being the mean at hospital admission) in the PaO₂/FiO₂ ratio. This assumes a standard deviation of 105 and a dropout rate of less than 10%.

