
Objective 2
 
Number of days with hypoxia (defined as SpO₂ <93% breathing room air or the dependence on supplemental oxygen after randomisation to Day 28 (or discharge, whichever comes earlier)
	
Use SpO₂ (%) and Suppl O₂ (Y/N) from Vital parameters to derive indicator variable which flags each day where this condition holds.
 
Derive variable per participant that gives total number of days with condition
	
Summary statistics of variable with Total number of days: n, mean, SD, median, minimum, maximum
 
By treatment arm

Endpoint	Derivation	Analysis

Objective 3 Duration of ventilator free days after randomisation to Day 28 (or discharge, whichever comes earlier)
	
Use data from Vital parameters (include all days, where NIV, IV and ECMO='N')
	
Summary statistics of variable with Total number of days: n, mean, SD, median, minimum, maximum By treatment arm

Objective 3 Duration of invasive mechanical (including ECMO) and non-invasive mechanical ventilation in ventilated participants
	
Complement of above (exclude participants who are not ventilated i.e. do not include these with a duration of 0)
	
Summary statistics of variable with Total number of days: n, mean, SD, median, minimum, maximum By treatment arm

Objective 3 Time since randomization until first use of high-flow oxygen devices or non-invasive mechanical ventilation or invasive mechanical ventilation or ECMO in non-ventilated participants (i.e. excluding participants who are ventilated within 24h prior to or after randomization) during 28-day assessment period
	
Use Vital Parameter CRF and the method of supplementary oxygen variable. Use the date from this CRF to identify when first use occurred. Indicator variable to identify sub-group to be included. Censor if never used any of these ventilation methods at Day 28
	
Kaplan-Meier analysis using PROC LIFETEST. Strata ACTARM. Request Survival plot adjusting axis and heading titles to reflect progression and not response Output statistics: Appropriate statistics from analysis as indicated in mock shell

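### Ventilation duration is summarised by arm only in participants who were ventilated, a subset treatment can change, so the figures are not a randomised comparison and could mislead in either direction

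*SAP*

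**What the plan says.** SAP 8.2, Table 8.1, has two adjacent rows built from the daily vital-parameter records.

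- **Ventilator-free days.** These count days on which non-invasive ventilation (NIV), invasive ventilation (IV) and ECMO are all recorded 'N', up to Day 28 or discharge if earlier. No rule is given for death or for days after discharge.
- **Duration of ventilation.** The derivation is "Complement of above (exclude participants who are not ventilated i.e. do not include these with a duration of 0". The same instruction stands in SAP 2.2.1.2.

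Both rows are reported as n, mean, SD, median, minimum and maximum by arm, with no model, difference or interval.

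Protocol 4.3 lists the endpoint as exploratory: "Duration of invasive mechanical (including ECMO) and non-invasive mechanical ventilation in ventilated patients". The SAP, written against protocol version 3.0, lists it with the secondary endpoints. SAP 3.1 plans no p-values for endpoints of the secondary objectives, but promises 95% confidence limits for comparisons of interest.

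Protocol 3.2 and SAP 2.1.2 make progression to mechanical ventilation a secondary objective. Protocol 6.2 excludes only invasive ventilation lasting more than 24 hours at randomisation, so some participants are already ventilated at entry.

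**The concern.** Randomisation makes the arms comparable as randomised. It does not make the ventilated part of one arm comparable with the ventilated part of the other when treatment may affect who is ventilated. Participants ventilated at entry belong to the subset whatever the treatment does. The rest enter it through an outcome.

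A drug that keeps some people off the ventilator changes the mix of courses left in its own arm, and the mean of those left can move either way. A reader who compares the two columns could conclude that the drug lengthens ventilation, does nothing, or helps more than it does, while the ventilation used per randomised participant says something else. That burden matters here because protocol 3.1 justifies the trial by pressure on ICUs.

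Protocol 4.2 contains no endpoint dedicated to progression to, or duration of, ventilation. The secondary objective on ventilation therefore rests mainly on the rows in protocol 4.3.

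**Working it through.** **1. The plan's own figure.** No design figure exists for ventilation. The only one is for PaO2/FiO2: "there would be >85% power" with 54 against 27, a difference of 80 and an SD of 105.

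- SE = 105 × √(1/54 + 1/27) = 24.75. Then 80/24.75 − 1.96 = 1.27, which gives power of 89.8%.
- With 10% dropout (48.6 against 24.3), power is 86.6%. The t-based values are 89.1% and 85.7%.

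The figure reproduces. It supplies the arm sizes used below but says nothing about ventilation.

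**2. Proportion ventilated.** Protocol 2.2 gives about 5% of infected patients invasively ventilated and 15-20% admitted. If all ventilated patients are admitted, this implies 5/20 = 25% to 5/15 = 33% of admissions, or about 7 to 9 of 27 controls. The endpoint also counts non-invasive ventilation, so the true share may be higher.

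**3. Formula.** Let p be the proportion ventilated under control, m their mean duration, q the share of those courses the drug prevents, and s the mean length of the prevented courses.

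- Ventilated-only difference (drug minus control) = q(m − s)/(1 − q)
- All-participant difference = −p·q·s

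The second is always in the drug's favour when courses are prevented. The first takes the sign of m − s.

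**4. Illustration.** Course lengths are not in the documents. Assume p = 30%, with half the courses lasting 6 days and half 15. Control: m = 10.5 days among the ventilated, and 0.15 × 6 + 0.15 × 15 = 3.15 days over all participants. Let the drug prevent half the courses (q = 0.5).

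| Courses prevented | s | Ventilated only, drug vs control | All participants, drug vs control |
|---|---|---|---|
| All the 6-day courses | 6 | 15.0 vs 10.5 (+4.5) | 2.25 vs 3.15 (−0.90) |
| Half, regardless of length | 10.5 | 10.5 vs 10.5 (0) | 1.575 vs 3.15 (−1.575) |
| All the 15-day courses | 15 | 6.0 vs 10.5 (−4.5) | 0.90 vs 3.15 (−2.25) |

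**5. Range for the short-course case.** Take 9 of 27 controls ventilated, short/long course lengths of 2/10, 3/15 or 5/20 days, one third to two thirds of courses short, and half or all of the short ones prevented. The ventilated-only difference runs from +1.1 to +10.0 days. The all-participant difference runs from −0.1 to −1.1.

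**6. Simulation.** 5,000 trials per scenario, 54 against 27, 25% or 33% ventilated. Course length is assumed lognormal (median 8 days, log-SD 0.9, limited to 1-28 days), with no deaths. Differences in mean days, drug minus control:

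| Assumed drug effect | Ventilated only | All participants |
|---|---|---|
| None | about 0 | about 0 |
| Prevents all courses of 5 days or less | +3.1 to +3.2 | −0.3 to −0.4 |
| Prevents half of those | +1.3 | about −0.2 |
| Prevents 30% regardless of length | about 0 | −0.9 to −1.1 |
| Prevents half of courses of 15 days or more | −1.7 to −1.8 | −0.8 to −1.0 |
| Shortens every course by 3 days | −1.7 | −0.7 to −1.0 |

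In the second scenario the drug arm looks worse in 79-82% of trials. In the last, courses cut to zero leave the subset, so a 3-day shortening shows as about 1.7 days.

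**7. The row above.** A never-ventilated participant discharged on day 8 scores about 8 ventilator-free days. One who stays 28 days with 5 ventilated days scores about 23, so the worse course gets the better score.

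The word 'complement' is also open. Someone ventilated for 2 days and discharged on day 10 has 8 ventilator-free days. The complement is 2 within observed days, but 28 − 8 = 20 out of 28.

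**The case against.** **The row is descriptive and honestly labelled.** The endpoint's name says it concerns ventilated participants. No contrast or p-value is planned for it, and the current protocol calls it exploratory. This stands and limits the seriousness. Means printed side by side by arm still invite comparison.

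**Nothing is lost.** Because n is tabulated, n × mean / arm size recovers the all-participant mean: 30% × 10.5 = 3.15 and 15% × 15 = 2.25. That is correct, but it leaves the valid comparison for the reader to reconstruct, and no interval is printed.

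**Other rows cover ventilation.** A reader might infer that this is the only endpoint on the amount of ventilation. The documents do not support that. Ventilator-free days has no ventilated-only restriction. The daily ordinal-scale charts and the area-under-the-curve score include everyone and carry death and discharge forward. Time to first use of respiratory support has its own Kaplan-Meier analysis.

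None of these is a clean substitute. Ventilator-free days has the faults shown above. Ordinal category 3 merges non-invasive ventilation with high-flow oxygen. The area score mixes all levels of support. Time to first use also pools high-flow oxygen, leaves out those ventilated around randomisation, and gives timing rather than amount.

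**Keeping zeros creates a problem of its own.** A participant ventilated for one day who then dies would score 1 day. This stands, and the remedy has to deal with death directly.

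**Conclusion.** The point holds as a recommended change to one descriptive, exploratory row. The by-arm ventilated-only durations are not a randomised comparison, and no other planned row replaces them cleanly.

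A reader might go further and infer that the rule works against the drug. The documents do not support that: they give no course lengths and do not say which courses would be prevented. The drug arm looks worse only if the prevented courses are shorter than average. Prevention regardless of length hides the benefit, and prevention of long courses can flatter the drug. Early deaths could shift either arm.

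The sizes given (+4.5 against −0.9 days in the main illustration, about +3 against −0.3 to −0.4 in the simulation) rest on assumed course lengths and an assumed pattern of prevention. Certain are the loss of comparability if treatment affects who is ventilated, and the formula for its direction.

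**What to change.** In SAP Table 8.1, and to match in SAP 2.2.1.2:

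1. For every participant in the Full Analysis Set, count days to Day 28 recorded as NIV, IV or ECMO = 'Y'. Do not derive this as 28 minus ventilator-free days. Enter 0 for those never ventilated and 0 for days after discharge alive. State the rule for days after transfer or withdrawal.
2. Report by arm the number and percentage ventilated, and the between-arm difference in mean ventilated days with a 95% CI, as SAP 3.1 already foresees for comparisons of interest.
3. Handle death explicitly. Show 28-day deaths beside this result, and add a summary that scores death by Day 28 as the worst outcome. One example is ventilator-free days out of 28, with 0 for death and with days after discharge alive counted as ventilator-free.
4. Keep the ventilated-only duration as description, labelled as a non-randomised comparison.

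The cost is one extra derivation and table from daily records already collected, plus written rules for death, discharge and transfer. No new data are needed, and the primary analysis and sample size do not change.

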3.2. Secondary Objectives

- to study if early intervention with Zilucoplan® is safe (number of AEs/SAEs)
- to study if early intervention with Zilucoplan® affects clinical outcome defined by duration of hospital stay, 6-point ordinal scale, time to defervescence, supplemental oxygen use and SOFA score
- to study if early intervention with Zilucoplan® affects progression to mechanical ventilation and/or ARDS and duration of ICU stay
- to study if early intervention with Zilucoplan® affects the rate of nosocomial infection
- to study if treatment with Zilucoplan® has a favourable effect on long term at follow up 12-22 weeks post-randomization
- to study if treatment with Zilucoplan® affects all-cause mortality rate at day 28 and at 12-22 weeks post-randomization

4. End Points + Time Points

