6.1. Inclusion Criteria

-Recent (≥ 6 days and ≤ 16 days of flu-like symptoms or malaise prior to randomization) infection with COVID-19.

-COVID-19 diagnosis confirmed by antigen detection test and/or PCR and/or positive serology, or any emerging and validated diagnostic laboratory test for COVID-19 within this period. For patients with a negative SARS-CoV-2 PCR and either a positive SARS-CoV-2 antigen or antibody test, the presence of suggestive lesions for COVID-19 on chest-CT scan is mandatory.

-In some patients, it may be impossible to get a confident laboratory confirmation of COVID-19 diagnosis after 24h of hospital admission because viral load is low and/or problems with diagnostic sensitivity. In those cases, in absence of an alternative diagnosis, and with highly suspect bilateral ground glass opacities on recent (< 24 h) chest-CT scan (confirmed by a radiologist and pulmonary physician as probable COVID-19), and a typical clinical and chemical diagnosis with signs of cytokine release syndrome, a patient can be enrolled as probable SARS-CoV-2-infected. In all cases, this needs confirmation by later seroconversion.

-Presence of hypoxia defined as

1) O₂ saturation below 93% on minimal 2l/min O₂ therapy;
and/or

2) PaO₂/FiO₂ below 350 mmHg (Strongly recommended: patient in upright position, after minimal 3 minutes without supplemental oxygen; In ventilated patients PaO₂ can be taken from invasive arterial line and FiO₂ taken directly from mechanical ventilation settings).

-Signs of acute lung injury and/or cytokine release syndrome defined as

ANY of the following

-serum ferritin concentration > 1000 mcg/L and rising since last 24h

-single ferritin above 2000 mcg/L in patients requiring immediate high flow oxygen device (Optiflow) or non-invasive or invasive mechanical ventilation

-lymphopenia defined as < 800 lymphocytes/microliter and two of the following extra criteria

-Ferritin > 700 mcg/L and rising since last 24h

-increased LDH (above 300 IU/L) and rising since last 24h

-D-Dimers > 1000 ng/mL and rising since last 24h

-CRP above 70 mg/L and rising since last 24h and absence of bacterial infection

-if three of the above are present at admission, no need to document 24h rise

-Low dose Chest CT or HRCT or Angio Chest CT scan showing bilateral infiltrates within last 2 days prior to randomization

-Admitted to specialized COVID-19 ward or an ICU ward taking care of COVID-19 patients

-Age ≥ 18 years

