- Number and percentage of signs of Cytokine Syndrome (should be 100%)
 - As shown by:
 - Number and percentage of single ferritin >2000 ng/ml (denominator participants with high flow nasal oxygen or mechanical ventilation i.e. total of participants on ordinal score 2 or 3 (which should be our participant population)) OR
 - Number and percentage of Ferritin > 1000 ng/ml and rising since last 24 hours
OR
 - Lymphopenia < 800 /μL AND ≥ 2 of:
 - Ferritin > 700 mcg/L and rising since last 24h

- CRP > 70 mg/dL and rising since last 24h without bacterial infection
- LDH > 300 IU/L and rising since last 24h
- D-dimers > 1000 ng/mL and rising for 24h

OR

- Lymphopenia < 800 / μ L AND \geq 3 of:
 - Ferritin > 700 mcg/L
 - CRP > 70 mg/dL
 - LDH > 300 IU/L
 - D-dimers > 1000 ng/mL

Summary statistics and distribution plots of laboratory parameters listed here will be provided by treatment arm.

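### The time-to-respiratory-support endpoint counts high-flow oxygen as an event without clearly excluding patients already on it, and no Table 8.1 row gives time to mechanical ventilation

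*SAP*

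**What the plan says.** SAP section 8.2, Table 8.1 (Objective 3) defines the endpoint as "Time since randomization until first use of high-flow oxygen devices or non-invasive mechanical ventilation or invasive mechanical ventilation or ECMO in non-ventilated participants", with the restriction "excluding participants who are ventilated within 24h prior to or after randomization". The table in SAP 2.2.1.2 has the same definition. So does protocol 4.3, where it is an exploratory endpoint: "in non-ventilated patients (i.e. excluding patients who are ventilated within 24h prior to or after randomization) during 28-day assessment period". Time runs from randomisation (SAP 2.2.1.2).

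The derivation takes the date of first use from the Vital Parameter form. It asks for an indicator of the subgroup to include, without giving the rule, and ends: "Censor if never used any of these ventilation methods at Day 28". The analysis is Kaplan-Meier by arm. SAP 3.1 plans confidence limits and no p-values for secondary objectives.

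The objective served is whether treatment "affects progression to mechanical ventilation and/or ARDS and duration of ICU stay" (protocol 3.2). Patients on high-flow oxygen can be enrolled; one route in protocol 6.1 is "single ferritin above 2000 mcg/L in patients requiring immediate high flow oxygen device (Optiflow) or non-invasive or invasive mechanical ventilation".

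**The concern.** High-flow oxygen is in the event list but is not named in the exclusion. If *ventilated* does not cover it, a patient randomised while on high-flow oxygen enters the analysis with the event already present. The treatment cannot influence that event, yet it counts in both arms and dilutes the comparison.

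A second problem does not depend on how the word is read. The step from high-flow oxygen to intubation is central to an objective about progression to mechanical ventilation. This endpoint cannot see that step in patients who start on high-flow oxygen.

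**Working it through.** **1. The plan's own figure.** None is stated for this endpoint. The only design figure is power above 85% for PaO2/FiO2 (54 vs 27, difference 80, SD 105, two-sided 5%). It reproduces under the normal approximation at 89.8%, or 86.6% after 10% dropout, and this point does not affect it.

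**2. Event list against exclusion.**

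| Support at randomisation | In event list | Excluded, reading 1 (ventilated = non-invasive, invasive, ECMO) | Excluded, reading 2 (high-flow also covered) |
|---|---|---|---|
| High-flow oxygen | yes | **no** | yes |
| Non-invasive or invasive ventilation | yes | yes | yes |
| Low-flow or no oxygen | no | no | no |

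**3. Which reading fits better.**
- For reading 1: ventilator-free days in the same table use "include all days, where NIV, IV and ECMO='N". The next row, duration of ventilation in ventilated participants, is the complement of that. The ICU-stay and mortality rows name high-flow devices separately when they mean them.
- For reading 2: the censoring sentence in this row, "Censor if never used any of these ventilation methods at Day 28", refers back to the whole event list, high-flow oxygen included.
- Reading 1 is the more natural. Reading 2 cannot be ruled out.

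**4. A patient on high-flow oxygen at entry, intubated on day 5.** On reading 1 the event falls on the first record. If first use came before randomisation, the time is negative, and the row has no rule for that. On reading 2 the patient is excluded. Either way the intubation does not enter the endpoint. If the same patient is intubated within 24 h after randomisation, the window removes the patient altogether. That is an exclusion on a post-randomisation outcome in an open-label trial.

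**5. Size on reading 1.** Let h be the share of the analysed set on high-flow oxygen at entry, equal in both arms, and p the 28-day event risk in the others.

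Analysed risk = h + (1−h)p, so the difference between arms = (1−h)(p_control − p_active).

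The documents give neither h nor p. I assume p = 40% (control) and 20% (active), and h from 10% to 50%. At h = 20%, for example, control is 0.20 + 0.80 × 0.40 = 0.52 and active is 0.20 + 0.80 × 0.20 = 0.36.

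The last two columns give simulated power of a two-sided 5% log-rank test (54 vs 27, 1,500 runs per h, nobody excluded as ventilated). They serve only as a measure of lost information, since no test is planned.

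| h | Control | Active | Difference (points) | Power, high-flow patients kept | Power, removed |
|---|---|---|---|---|---|
| 0 | 40% | 20% | 20 | about 50% | about 50% |
| 10% | 46% | 28% | 18 | about 36% | about 47% |
| 20% | 52% | 36% | 16 | about 29% | about 43% |
| 30% | 58% | 44% | 14 | about 20% | about 40% |
| 40% | 64% | 52% | 12 | about 16% | about 36% |
| 50% | 70% | 60% | 10 | about 11% | about 29% |

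At h = 20%, events present at entry make up 0.20/0.52 = 38% of control events and 0.20/0.36 = 56% of active events.

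**6. What is missed on either reading.** If 20% to 40% of patients enrolled on high-flow oxygen were later intubated (an assumption), the endpoint would miss about 3 to 6 intubations at h = 20% (81 × 0.20 = 16.2 patients; × 0.20 = 3.2; × 0.40 = 6.5). At h = 40% it would miss about 6 to 13 (32.4 patients; 6.5 to 13.0).

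**7. Whether another row fills the gap.** No Table 8.1 row gives time to mechanical ventilation. Ventilator-free days and ventilation duration receive summary statistics only. Time to ARDS does not isolate ventilation, because protocol 4.3 allows the ARDS criteria to be met on high-flow oxygen at 50 L/min or more. The row on not deteriorating calls a participant stable unless the change is below −1, so a move from score 3 to score 2 counts as stable.

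**The case against.** The strongest reply is that the text shows an undefined term and no more. The row itself groups high-flow oxygen with the ventilation methods, SAP 2.2.4.3 records the ventilation method with flow rate, and the subgroup rule may be in the mock table shells, to which SAP 8.2 defers detail and which are not among the documents. Where the SAP intends a time of zero, as in the last-fever row, it says so. This stands: a reader might infer that patients on high-flow oxygen are definitely events at time zero, and the documents do not settle that.

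A reader might also infer that their later intubation is never counted, or that this is the only endpoint for the objective. The documents do not support either inference. Objective 3 also has ventilator-free days, ventilation duration, time to ARDS and ICU stay, and later intubation also shows in the change in ordinal score and the daily chart of score categories. The gap is confined to time to mechanical ventilation.

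Nor does SAP 6.2 supply a value for h. Its remark "total of participants on ordinal score 2 or 3 (which should be our participant population" sits inside the denominator for one ferritin criterion, and score 3 pools high-flow oxygen with non-invasive ventilation.

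Finally, aligning the exclusion does not recover the lost intubations; only an added analysis does. That is correct, and it is why the fix has two parts.

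**Conclusion.** The concern holds as a mismatch between event list and exclusion that the wording leaves unresolved. On the more natural reading, the arm difference shrinks by the factor (1−h): 20 points becomes 16 at h = 20% and 12 at h = 40%. Those figures rest on assumed risks, an assumed share and equal shares in the two arms; the factor itself does not depend on the assumed risks. On the other reading there is no dilution. On both, escalation from high-flow oxygen present at entry is absent from this endpoint, and no other row supplies it as a time to event.

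The consequence is limited. The endpoint is secondary in the SAP, exploratory in protocol v6.0 and reported without a p-value. It touches neither the primary analysis nor the sample size. The change is still worth making, because the data are collected daily in hospital and the two readings produce different datasets.

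**What to change.** In SAP 2.2.1.2 and Table 8.1, and in protocol 4.3:

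1. Make the exclusion match the event list, using status at randomisation: exclude participants already on high-flow oxygen, non-invasive ventilation, invasive ventilation or ECMO. Drop the window that extends 24 h after randomisation, so that support started after randomisation counts as an event. State the rule for the subgroup indicator.
2. Add a Kaplan-Meier analysis of time to first invasive ventilation or ECMO in all participants on neither at randomisation. Count deaths before ventilation as events, or treat death as a competing event with cumulative incidence in place of Kaplan-Meier.

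The cost is some wording and one more table and plot from Vital Parameter data already collected. The downside is fewer patients in the composite that includes high-flow oxygen.
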